### **Data Collection**

The primary dependent variable is stimulant-free urine samples; all samples will be assessed using point-of-care test conducted at the center. Urine specimens will be collected for all participants at least once weekly throughout the study. Urine specimens are disposed of following recording of the result, thus, no samples are stored. Participants in the health education condition will receive \$10 for providing each urine sample (2x per week). Urine samples will be collected for participants in the financial incentives condition twice weekly for all 12 weeks of the intervention for which they can earn the incentives stated above by providing a negative urine sample. Participants in both conditions will also complete the questionnaires for decision making, demand for substances, craving, and treatment effectiveness at three additional times after baseline, at weeks 4, 8, and 12. Data for the questionnaires will be completed using pen and paper, then will be uploaded onto the computer and into REDCap. All participants will be compensated \$10 per assessment independent of substance use status to ensure high compliance.

### **Delivery of Financial Incentives**

All earned incentives will be provided to participants using a gift card or a PEX debit card, a reloadable debit card. The gift cards and PEX debit cards do not require a credit history check, and participants will pay no monthly fees for carrying the card. There are no costs for using the gift cards or PEX Debit Cards for instore or online shopping. Research staff or Safe Recovery staff will load money onto the participants gift or debit card after completion of an activity in which an incentive has been earned (i.e., completion of a urinalysis screening; negative urinalysis sample). We are choosing to use gift cards or PEX debit cards because they are easy to implement and money can be immediately loaded to the cards, thereby reducing the delay between the target behavior and delivery of the incentive, an important variable to maximizing the efficacy of the incentive.

### **Examining Intervention Acceptability**

At the 12-week assessment or shortly thereafter, participants in both the incentives for abstinence condition and psychoeducation plus usual care condition will complete a Study Acceptability Questionnaire (SAQ). This measure will be administered via pen and paper and will then be uploaded onto the computer into REDCap. The questionnaire will ask participants about the ease of use, helpfulness, and convenience of the intervention, as well as whether the intervention was fair, fun, and whether they would recommend it. Participants in the psychoeducation plus incentives condition will receive additional SAQ questions inquiring about whether they liked the incentives for abstinence and whether the incentives were helpful in terms of promoting stimulant abstinence.

Describe required screening procedures performed before enrollment and while on study.

As noted above, participants will be recruited primarily from Safe Recovery, a harm reduction facility located at the Howard Center in Burlington, Vermont. Individuals receiving services at Safe Recovery will be approached about participation by the Safe Recovery research staff. Potentially eligible participants will be asked when they come in for services if they would like to participate in a research study. If interested, prospective participants will be invited to complete the intake assessment.

**For research involving survey, questionnaires, etc.:** Describe the setting and the mode of administering the instrument and the provisions for maintaining privacy and confidentiality. Include the duration, intervals of administration, and overall length of participation.

Not applicable

All efforts will be made to maintain confidentiality. Assessments will be completed in a private room at Safe Recovery. Prospective participants who are eligible (i.e., participate in the Howard Center's syringe exchange program) will be approached by a study team member and asked about their potential interest in participating in the study. If interested, participants will then be provided with information about the study (via informed consent) and the study team member will review all steps on the consent process documentation sheet and answer any potential questions. If the participant consents to participate, then they will be asked to complete the following questionnaires. At intake, the Washington State syringe exchange health survey will be used to assess sociodemographic, substance use history, and substance use follow-back (McMahan et al., 2020). Demand for substances will be assessed using the simulated substance purchase task (Murphy et al., 2011). Decision making will be assessed using the Monetary Choice Questionnaire (Kirby et al., 1999). Substance craving will be assessed using the three-item craving scale (McHugh et al., 2021). The intake assessment will take no longer than 120 minutes and will occur once at the intake.

At weeks 4, 8 and 12 of the intervention, all participants will complete the Monetary Choice Questionnaire, three-item craving scale, and demand for substances using the simulated purchase task. Data for the questionnaires will be completed using pen and paper, then will be uploaded onto the computer and into REDCap. Each assessment will take no longer than 20 minutes.

All data will be coded by an assigned identification number, with the codes known only by the investigators on this project. Names will not be connected with any results. The security of the records will be maintained by keeping paper files in a locked file cabinet and by keeping REDcap computer files in password protected files. The master copy will be kept in a different locked file cabinet from the coded data. The results of this study will eventually be published, but patient confidentiality will be maintained.

**TYPES OF PROCEDURES** (Please do not use the "other" option unless the procedure is not listed.)

Check all that apply.

	Survey (mail, telephone, in-person, on-line)		Blood drawing:	Vol. 	Over days, weeks?		
	Medical exams/history				Type & Amt.		
	Deception *see below		Surgery				Collection of Urine and/or Feces
	Observation		Drug Administration				HIV Testing
	Photographs		Device Use				Ultrasound (e.g. echocardiogram)
	Audio Recording		Exercise				Imaging (e.g. CT scan, DEXA, mammogram, PET scans, SPECT)
	Video Recording		Diet				Use of Radiation treatment
	Interviews in person or by phone		Pathology Specimens (retrospective)				Use of Radioactive substances (e.g. radiolabeled antibodies, drugs or contrasts)
	Focus Groups		Genetic Materials (DNA)** see below				MRI (for treatment studies)
	Review of prospective data		Questionnaires				MRI (not for treatment studies)
	Review of retrospective data		Diaries				Tissue (obtained for clinical purposes)

	Recording of Identifiable Data		Pregnancy Tests		Tissue (obtained solely for research )
	Electrocardiograms				
	Sensitive Data (criminal or sexual conduct, drug or alcohol conduct or use)	(specify):			

**\*\*If genetic information is being collected, GINA language must be added to the consent form.**

\*Deception typically involves withholding information from the potential subject and would require an alteration to the consent process.

**Statistical Considerations:** Delineate the precise outcomes to be measured and analyzed. Describe how these results will be measured and statistically analyzed. Delineate methods used to estimate the required number of subjects. Describe power calculations if the study involves comparisons. Perform this analysis on each of the primary and secondary objectives, if possible.

Participant baseline demographics and characteristics will be compared between treatment conditions (Health Education vs. health Education plus Incentives for Abstinence) using Chi Square Tests of Independence or Fisher's Exact Tests for categorical variables and Wilcoxon Rank Sum Tests or Two-Sample T-tests for continuous variables, depending on the distributions of the variables. If a specific characteristic differs significantly between treatment conditions and is predictive of the outcome, it will be considered as a potential covariate in subsequent analyses. The primary outcome to be analyzed will be point-prevalence stimulant abstinence, which will be determined by percentage of negative urine samples for stimulants using a point-of-care test. Analyses of treatment condition effect on point-prevalence stimulant abstinence will adhere to an intent-to-treat approach whereby all participants randomized to each treatment condition will be included in the analyses independent of early dropout, noncompliance, etc. Point-prevalence abstinence rates will be compared between treatment conditions at individual timepoints using Chi Square Tests of Independence. Comparisons of point-prevalence abstinence rates between treatment conditions across all assessments will be analyzed using mixed model repeated measures for categorical data based on generalized estimating equations (GEE) using a logistic link function. Comparisons of predictors of abstinence that are continuous outcomes and continuous outcomes based on survey responses between treatment conditions across all assessments will be analyzed using mixed model repeated measures analyses of variance. Comparisons of predictors of abstinence that are categorical outcomes and categorical outcomes based on survey responses between treatment conditions across all assessments will be analyzed using mixed model repeated measures for categorical data based on generalized estimating equations (GEE) using a logistic link function.

Because this is an exploratory pilot study evaluating the potential efficacy, feasibility, and acceptability of a contingency management intervention for stimulant use within a syringe exchange program, we are proposing a small, initial pilot study of 40 participants. Data from a previous meta-analysis study (Bolívar et al., 2021), which examined the CM treatment effects on abstinence from psychomotor stimulant use found a mean effect size for treatment effect on abstinence from psychomotor stimulant of Cohen's  $d = 0.70$ . However, among studies included in this analysis, the minimum effect size which was for the outcome of point-prevalence stimulant abstinence was Cohen's  $d = 0.51$  ([name] et al., 2002; doi:10.1001/archpsyc.59.9.817). Using this "medium" effect size for sample size calculation, in order to detect a statistically significant difference in point-prevalence stimulant abstinence between treatment conditions with 80% power, with 2-sided significance level alpha of 0.05, a total sample size of 88 participants would be required. However, because this is an initial pilot study looking to assess feasibility and potential efficacy, we expect to observe discernable differences between the two conditions with a sample size of 40. The goal is to conduct a pilot study where the data could then be used to inform a larger, fully powered randomized control trial.

**Risks/Benefits:** Describe any potential or known risks. This includes physical, psychological, social, legal or other risks. Estimate the probability that given risk may occur, its severity and potential reversibility. If the study involves a placebo or washout period, the risks related to these must be addressed in both the protocol and consent. Describe the planned procedures for protecting against or minimizing potential risks and assess their likely effectiveness. Where appropriate, discuss plans for ensuring necessary medical or professional intervention in the event of adverse effects to the subjects. Discuss the potential benefits of the research to the subjects and others. Discuss why the risks to the subjects are reasonable in relation to the anticipated benefits to subjects and others. Discuss the importance of the knowledge gained or to be gained as a result of the proposed research and why the risks are reasonable in relation to the knowledge that reasonably may result. If there are no benefits state so.

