### **Intake Assessment**

All prospective participants will complete a formal assessment at intake; participants will receive \$25 for completing the assessment. The screening will take no more than 2 hours. Prior to completing the intake assessment, the prospective participant will read through and sign the consent form; the consent form will contain information about the intake assessment and its procedures, along with the study procedures. During the intake, questionnaires will be completed using pen and paper, then will be uploaded onto the computer and into a secure web platform, REDCap. The assessment battery will include questionnaires that assess the following six areas: (1) sociodemographic, (2) substance use history, (3) substance use follow-back, (4) substance craving, (5) demand for substances, and (6) decision making. The first 3 areas will be assessed using the WA state syringe exchange survey and Treatment Effectiveness Assessment. Substance craving will be assessed using the three-item craving scale. Demand for substances will be assessed using the simulated substance purchase task. Decision making will be assessed using the monetary choice questionnaire. For additional detail about each measure, see each respective questionnaire. Participants will receive \$25 for their time and participation in completing the intake assessment.

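### A covariate enters only if the randomised arms differ significantly on it and it predicts outcome; none is named, so any one prognostic intake measure will almost always go unused (modest cost)

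*Combined protocol and SAP*

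**What the plan says.** Statistical Considerations first compares baseline characteristics between arms with significance tests (chi-square or Fisher for categorical variables, Wilcoxon or t for continuous ones). It then states: "If a specific characteristic differs significantly between treatment conditions and is predictive of the outcome, it will be considered as a potential covariate". Two conditions must both hold, and even then the variable is only considered. The section gives no alpha for the baseline tests. It does not say whether *predictive* is to be tested in the trial data or known beforehand.

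Abstinence is analysed in two ways. One is visit by visit: "Point-prevalence abstinence rates will be compared between treatment conditions at individual timepoints using Chi Square Tests of Independence". The other pools visits: "Comparisons of point-prevalence abstinence rates between treatment conditions across all assessments will be analyzed using mixed model repeated measures for categorical data", implemented as a GEE with a logistic link. No covariate is named for either, and no stratification factor is named for randomisation.

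Candidate measures exist. Under Intake Assessment, "The assessment battery will include questionnaires that assess the following six areas", and "Substance craving will be assessed using the three-item craving scale". The survey-procedures text adds that the "syringe exchange health survey will be used to assess sociodemographic, substance use history, and substance use follow-back".

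The sample-size paragraph plans 40 participants and says that "the data could then be used to inform a larger, fully powered randomized control trial".

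**The concern.** Prespecified adjustment is useful because a prognostic baseline variable removes outcome variance, whether or not the arms happen to differ on it. This rule instead makes a significant difference between arms a requirement. In a randomised trial such a difference arises only by chance, so a strongly prognostic measure is normally left out.

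Two things are at stake. The efficacy model stays open until data are seen: two analysts could reasonably report different adjustment sets from the same data. And the reported interval does not gain the precision that a prognostic intake measure could give. Both matter because the pilot's estimate and interval are meant to inform the next trial.

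**Working it through.** **Inputs.** From the plan: N = 40, two randomised arms, d = 0.51 (the effect used in the sample-size paragraph), two-sided 0.05 for the efficacy test. Assumed: 20 per arm, alpha 0.05 for the baseline tests (0.10 as a variant), and a baseline-outcome correlation rho, which the documents do not give and which is shown as a range. Eligibility requires stimulant use in the past 30 days and a moderate or severe disorder, which may restrict rho.

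**The plan's own figure.** The plan gives no number for covariate selection. Its only design figure is a total of 88 at d = 0.51. The usual normal formula gives 2 × (1.96 + 0.842)² / 0.51² = 60.4, so 61 per arm and 122 in total; 88 is not reproduced. That is a separate matter and nothing below uses it.

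**Step 1: how often one given measure is used.** P(used) = P(significant imbalance) × P(predictive | imbalance) ≤ alpha. So P(unused) is at least about 1 − 0.05 = 95%, or 1 − 0.10 = 90%. Actual test sizes at 20 per arm agree: t about 5.0%, Wilcoxon 4.9%, Fisher 1.2-2.5%, uncorrected chi-square 3.9-5.3% (prevalence 0.1 to 0.5). If *predictive* is also tested in the data, simulated use is 1.3%, 2.3%, 3.5% and 4.2% at rho 0.2, 0.3, 0.4 and 0.5.

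**Step 2: several measures screened.** With six independent characteristics, P(at least one significant imbalance) = 1 − 0.95⁶ = 26%. Six is illustrative: the plan lists six areas, not six variables.

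**Step 3: power and interval width, one measure.** The proxy is a continuous outcome in SD units under a linear model (60,000 simulated trials for power, 12,000 for width). Range under the rule covers both readings of *predictive*.

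| rho | Power, unadjusted | Power, rule | Power, prespecified | Width, rule | Width, prespecified |
|---|---|---|---|---|---|
| 0.2 | 35.1% | 34.8-34.9% | 35.5% | 1.27-1.28 | 1.265 |
| 0.3 | 34.6% | 34.2-34.5% | 36.8% | 1.27-1.28 | 1.230 |
| 0.4 | 34.9% | 34.5-34.8% | 39.5% | 1.27-1.28 | 1.182 |
| 0.5 | 35.1% | 34.8-34.9% | 43.3% | 1.27-1.28 | 1.118 |

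Hand check: the unadjusted standard error is √(2/20) = 0.316, and 2 × 2.02 × 0.316 = 1.28, close to the simulated 1.27. Adjustment multiplies width by about √(1 − rho²): at rho 0.5, 1.27 × 0.866 = 1.10, against 1.118 simulated. The ratio 1.118/1.10 = 1.016 is the price of the extra term. Break-even is where √(1 − rho²) = 1/1.016 = 0.984, that is rho = √(1 − 0.984²) = 0.18.

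**Step 4: six measures screened (same proxy).** A covariate enters in 6-13% of trials if *predictive* is tested and in about 26% if it is prior knowledge. Power at rho 0.2 is 33.6-35.3% under the rule, 35.1% unadjusted and 35.8% with one prespecified measure. At rho 0.3 it is 32.3-34.6%, 34.9% and 36.8%. Root mean squared error at rho 0.3 is about 0.30 under the rule (0.296-0.308 across runs and readings), 0.314-0.315 unadjusted and 0.303 prespecified. The reported standard error under the rule stays at 0.314-0.317.

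**Step 5: validity.** Null rejection under the rule is 0.042-0.050 with one measure (rho 0.1-0.5) and 0.036-0.050 with six.

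**Step 6: logistic GEE, illustrative only.** This assumes a control rate of negative samples of 28% (15% as a variant), random-effect SD 1-3, 12 or 24 visits, and a Mancl-DeRouen standard error with a t reference. For one measure, prespecified minus rule is −1 to 0 points of power at rho 0.2, +1 to +2 at 0.3, about +4 at 0.4 and +8 to +9 at 0.5. Null rejection is 0.034-0.057 with the correction. With the uncorrected sandwich it is 0.057-0.078 unadjusted and 0.063-0.083 adjusted.

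**The case against.** The strongest reply is that this is an exploratory pilot, knowingly below its own stated sample size, and that the benefit hangs on a correlation the documents never give. At rho 0.2 or lower, prespecifying gains nothing or loses about a point: in the illustrative GEE with six characteristics screened it gives 31.1% against 31.6% unadjusted at rho 0.2, and 29.4-29.6% against 30.8-30.9% at rho 0-0.1. Nothing in the plan shows that craving or any other intake score reaches 0.4 or 0.5. The GEE results also rest on control rates that are not in the documents. All of this stands, and it limits the point to a modest one.

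A second reply is that adjusting for an observed imbalance has some merit. It does. With six prognostic measures screened, the rule slightly lowers the true error of the estimate. A reader might therefore go too far in inferring that deleting the rule costs nothing at any correlation, or that the rule never does as well as an unadjusted model; Step 4 contradicts both. What remains against the rule is that the reported standard error does not fall, so the interval does not show that gain.

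Third, the plan says considered, not entered, while the simulations enter every qualifying variable. That makes them approximate, but the latitude is itself the open choice at issue.

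**Conclusion.** The point holds as a modest improvement. The 95% figure is per measure and follows from randomisation and an assumed alpha of 0.05. The power and width gains depend on rho: close to nil at 0.2, about 2-3 points of power and 3% of width at 0.3, and about 8-9 points and 12% at 0.5 (continuous proxy, 20 per arm, d = 0.51).

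A reader might infer that choosing covariates this way inflates type I error or invalidates the trial. It does not: null rejection stays at or slightly below 5%, and the unadjusted comparison is valid. A reader might also infer that only the GEE can carry a covariate. That is true of the two abstinence comparisons, but the mixed models for survey outcomes could carry one too. The plan does not rank the GEE against the visit-by-visit tests; that is a separate question, and this point does not depend on it.

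**What to change.** In Statistical Considerations, replace the covariate sentence with text to this effect:

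- Before outcomes are seen by arm, one graded intake measure judged prognostic is named: stimulant-use frequency if the intake survey records it, otherwise another intake score such as the three-item craving scale. A yes/no item on past-30-day use cannot serve, because every eligible participant meets it.
- That measure is included in the across-assessments abstinence GEE whether or not it differs between arms. The unadjusted GEE is reported as a sensitivity analysis.
- Baseline comparisons are descriptive and do not select covariates.
- The GEE uses a small-sample-corrected robust standard error (for example Mancl-DeRouen with a t reference), because the uncorrected sandwich is somewhat anti-conservative at 40 participants.

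The cost is a few sentences, a check of what the intake survey records, one model term and a software option for the correction. Downsides to state openly: one degree of freedom; a conditional rather than marginal odds ratio (median 2.19 against 2.00 at rho 0.5 in the illustrative GEE); and no gain, or about 1 point of power lost, if the measure is only weakly prognostic (rho about 0.2 or lower). No new data collection is needed if an existing intake score is used.

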### **Intervention Conditions**

Participants will be randomly assigned to one of two intervention conditions. These sessions will be administered by one of the following study team members: Howard Center research assistants, UVM research assistants helping with the project, or Drs. [name] and [name].

**Health Education Condition.** The Health Education condition is based on a previous intervention used as a control in a number of other studies (Mooney et al, 2013). Sessions consist of an educational program addressing a variety of health, wellness, and lifestyle topics adapted from a previously implemented wellness manual. One education topic will be discussed each day. The 12 daily educational topics will include: (1) stress relief, (2) nutrition, (3) hepatitis prevention, (4) HIV prevention, (5) sleep hygiene, (6) health screening, (7) meditation, (8) home emergencies, (9) healthy relationships, (10) common medical problems of people who use drugs, (11) strategies to reduce anxiety, depression and other negative moods, and (12) self-defense. Participants in this condition will be scheduled for two clinic visits per week for 12 weeks. Thus, the health education on the 12 topics listed above will be provided in addition to the services provided to all individuals in the Howard Center Safe Recovery program. At one session each week, the individual will meet with a study team member listed above who will review a topic handout with the participant. We anticipate these sessions will take approximately 10-15 minutes.

**Health Education plus Incentives for Abstinence.** Participants in the experimental condition will have the opportunity to earn financial incentives for abstaining from stimulant use, in addition to receiving the same health education as the control condition. Monitoring of stimulant use will occur through twice-weekly urinalysis during the 12 weeks of the intervention. Specimens will be screened for stimulant use using a 10-panel point-of-care test taken at the center. The financial incentives will be contingent on negative samples for stimulants which include cocaine, methamphetamine, and amphetamine. The incentive amount will start at \$25 and increase for each subsequent stimulant-negative urine sample, up to \$65 per sample. Only tests where the display indicates negative samples will result in participants earning reinforcement. The incentive amount

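### Logistic GEE on 40 participants with no small-sample method named: the usual sandwich Wald test would reject somewhat above 5%, more so if abstinence is rare

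*Combined protocol and SAP*

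**What the plan says.** Statistical Considerations (under Methods and Procedures) defines the primary outcome as point-prevalence stimulant abstinence, measured by the percentage of stimulant-negative urine samples. It plans two analyses of that outcome:

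- By visit: "Point-prevalence abstinence rates will be compared between treatment conditions at individual timepoints using Chi Square Tests of Independence".
- Across all assessments: "mixed model repeated measures for categorical data based on generalized estimating equations (GEE) using a logistic link function".

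Neither is designated as the main comparison. For the GEE, the section does not state the working correlation, the variance estimator, whether the test is Wald or score, the reference distribution, how time enters the model, or any small-sample correction.

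On size, the same section says "we are proposing a small, initial pilot study of 40 participants". The allocation ratio is not given; Intervention Conditions says only "Participants will be randomly assigned to one of two intervention conditions". On the number of results per person, Data Collection says "Urine specimens will be collected for all participants at least once weekly throughout the study". Data Collection and the compensation section both describe twice-weekly samples for 12 weeks in each condition, so up to 24 per participant.

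**The concern.** The sandwich variance used with GEE is justified when there are many independent clusters. Here the cluster is the participant. There are 40 of them, about 20 per arm if allocation is equal, however many urine results each supplies. With so few clusters the sandwich standard error tends to be too small, and a z reference ignores the uncertainty in estimating it. Both push a Wald test above its nominal level and make its intervals too narrow.

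The GEE is the only planned comparison of the primary outcome that uses all the assessments. Aim 1 includes efficacy, and the results are meant to inform a larger trial. An interval that is too narrow, or a p-value that is too small, would carry into that planning. Low abstinence, where the problem is worst, is plausible: participants have moderate or severe stimulant use disorder, report recent use and are recruited from a syringe exchange.

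**Working it through.** **The plan's own figure.** The documents state no error rate for the GEE, so there is none to reproduce. The only computed figure nearby is the sample size: "with 2-sided significance level alpha of 0.05, a total sample size of 88 participants would be required". From the stated d = 0.51 and 80% power, the normal formula gives n per arm = 2(1.960 + 0.842)²/0.51² = 2 × 7.85/0.2601 = 60.4, so 61 per arm and 122 in total. The 88 is not reproduced. That is a separate matter and does not affect what follows.

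**Inputs**

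- From the documents: 40 participants; up to m = 24 samples each; logistic link; two-sided alpha of 0.05 (stated only for the sample-size calculation).
- Assumed, because the documents do not give them: n = 20 per arm; true abstinence of 10-40%, equal in both arms; within-person correlation 0.3-0.7; no dropout.

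**Formulas.** Let S_i be the number of negative samples for participant i. With complete data and a condition-only model, the GEE estimate is the difference in logits of the arm proportions:

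- p_a = mean(S in arm a)/m, and D = logit(p_1) − logit(p_2).
- Uncorrected sandwich variance per arm: v_a = Σ(S_i − mean S_a)² / [n m p_a(1 − p_a)]².
- Wald z test: reject if D²/(v_1 + v_2) > 3.841.
- Score test on the same GEE: with r_i = S_i − overall mean and c_i = ±0.5 by arm, reject if (Σ c_i r_i)² / Σ(c_i r_i)² > 3.841.
- Participant-level test: two-sample t-test on S_i/m with 38 df.

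The sum of squares in v_a is in effect divided by n = 20 rather than n − 1 = 19. That alone shrinks the standard error by √(19/20) = 0.975. Skewness at low abstinence shrinks it further.

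**Rejection rate when there is no effect** (beta-binomial data, 40,000 replicates, Monte Carlo error √(0.05 × 0.95/40,000) = 0.11 points):

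| True abstinence | Sandwich Wald z | Excess over 5% |
|---|---|---|
| 20-40% | 5.4-6.6% | 0.4-1.6 points |
| 15% | 7.0-7.5% | 2.0-2.5 points |
| 10% | 8.3-11.1% | 3.3-6.1 points |

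Over the same settings the t-test rejects 3.7-5.1% and the score test 3.9-5.3%. At 10% abstinence, Kauermann-Carroll or Mancl-DeRouen covariance with t(38) still rejects 6.2-9.8%.

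**A second data model agrees.** Latent-normal data, 12-24 assessments and 4,000 replicates give 5.3-6.1% at 40% abstinence, 6.2-7.1% at 20% and 8.2-10.0% at 10%. The mean sandwich standard error is 0.83-0.98 of the true sampling SD.

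**The cause is the number of participants.** In the second model, with 24 assessments and correlation 0.7, the uncorrected Wald test rejects as follows:

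| Participants contributing | 40% abstinence | 20% | 10% |
|---|---|---|---|
| 88 | 5.3% | 5.7% | 6.3% |
| 28 (assumed heavy loss) | 6.7% | 7.7% | 12.8% |

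**Power at 20% versus 40% abstinence** (beta-binomial, correlation 0.5): uncorrected Wald 49.2%, participant-level t-test 47.8%, a difference of 1.4 points. The score test loses about 1 point and the corrected GEE about 5-7.

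**The case against.** The strongest reply is that an unspecified choice is not an error. A reader might infer that the planned standard errors are too small and the planned test over-rejects. The documents do not support that as fact. They never say that a sandwich Wald z test will be used, and a score test on the same GEE holds its level. This stands, and the point is therefore conditional.

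Four further limits also stand:

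- **Not always inflated.** A reader might infer that the error always favours a false positive. With only three assessments the Wald test rejected 4.2-6.1%, falling below 5% at 10% abstinence. The plan's 12 to 24 urine results put it in the inflated range, but inflation is not a general law.
- **No condition-by-visit test is planned.** A joint Wald test of many such terms would behave badly with 40 participants. The plan states only a comparison between conditions across assessments, so that behaviour is no measure of how serious this point is.
- **The GEE is not named as the primary test.** Chi-square tests at individual timepoints are planned for the same outcome, and neither is ranked above the other.
- **This is an exploratory pilot.** No confirmatory decision rests on the p-value, and at 20-40% abstinence the excess is under 2 points.

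None of this removes the reason to specify the test. The plan leaves open the setting that fixes the error rate, the usual choice is the weaker one, and a better one costs almost nothing.

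**Conclusion.** The point holds as a conditional one about prespecification. With 40 participants and no small-sample method named, the plan permits a sandwich Wald z test. Its true size would be about 5-7% at 20-40% abstinence, 7-7.5% at 15% and 8-11% at 10%. The excess is modest in the first range and material only if abstinence is rare.

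The figures rest on equal allocation, 24 samples, correlation 0.3-0.7 and complete data. None of the abstinence rate, the correlation or the allocation ratio is in the documents. Heavy loss of participants would make the excess larger. This is a worthwhile, inexpensive improvement to a pilot analysis, and it does not invalidate the design.

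**What to change.** In Statistical Considerations:

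1. Name one 1-df condition contrast, averaged over the scheduled samples, as the main across-assessments comparison.
2. Take its p-value from a permutation test or t-test on each participant's percentage of negative samples, or from a GEE score test. The participant-level version also matches the outcome as the plan defines it.
3. State the working correlation and how time enters the GEE.
4. If Wald intervals from the GEE are reported, use a small-sample-corrected covariance (Kauermann-Carroll or Mancl-DeRouen) with a t reference on about 38 df. Note that these may still be too narrow if abstinence is near 10%.
5. Report any condition-by-visit results descriptively.

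The cost is a few lines of wording and standard software. Intervals become slightly wider. At 20% versus 40% abstinence, about 1 point of power is lost with the participant-level or score test, and about 5-7 points if the p-value comes from the corrected GEE.
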